- Adequate cognitive ability to complete the questionnaires, give consent for the study and follow the physical and diet instructions

Main Study Exclusion criteria:

- transplant of any other organ besides kidney alone or a combination of a kidney/pancreas

- non-ambulatory or significant orthopedic problems
- cardiac/pulmonary disease that contraindicate the physical training
- any contraindication to exercise testing per the American Heart Association
- unable to comply with the training program

Muscle Biopsy Inclusion:

- Age between 18 and 65 years
- Patients who have a brachial–cephalic arteriovenous fistula (AVF) in the elbow or brachial–basilic AVF in the arm
- Exercise Arm- the biopsy will only be performed once, after the 12 month exercise intervention is completed (which will be longer than 1 year post transplant surgery)
- Control Arm- this procedure will be performed once, around one year post transplant surgery (may occur at any time during the study)

Muscle Biopsy Exclusion:

- Patients that do not meet the inclusion criteria

Identifying potential subjects for recruitment:

A waiver for an alteration of consent and waiver of documentation of consent is being requested for review of medical records to identify potential patients for study recruitment and also for a telephone screening process for patients that response to a recruitment flyer. The principal investigator already has access to these records as part of daily care for all patients seen in clinic. This presents no more than minimal risk since this data will be kept confidential.

Moreover, as part of the telephone screening process for patients interested in this study there will be oral consent obtained to start the screening process in order to determine if the patients are eligible to be in the study. If the patients are eligible, they will be schedule for a visit where they will be consented to be in the study.

Randomization: All patients who meet the enrollment criteria will be randomized 4:1 to the GH group or the control group.

- GH group: patients will be treated for 12 months with the GH method (Appendix 1) for one hour twice a week

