Maximal aerobic capacity test (VO₂ max): For subjects over 55 yrs or that are classified as moderate to high risk according to ACSM's risk stratification scale, this will occur in the presence of a physician. We will use a modified Balke Treadmill protocol: the treadmill will be set at a constant speed (3.3 mph) while the incline is increased by 2% every two minutes. This protocol is selected to ensure that the elderly subjects will be able to perform a maximal aerobic test. For younger (18-35 yr) subjects, the test will begin at a 10% grade and increase 2% every 2 minutes. If maximal effort is not reached

by minute 10 and a 20% grade, speed will be increased by 0.3 mph until maximal effort is achieved.

Accelerometer: subjects will be given an accelerometer with instructions for use and be asked to wear it around their waist for 1 week while awake to measure their level of physical activity. This will be completed at baseline, 6 months and 12 months post-intervention.

Muscle Biopsy

Optional muscle biopsies for GH group and control group, will be performed to measure expression of mature microRNAs using total RNA extraction, which will help evaluate how targeted exercise may change muscle development. The muscle biopsy will be performed by [name], [name], [name], and/or [name], all of which are experienced surgeons with prior experience performing muscle biopsies. The muscle biopsy will be performed at the University of Illinois at Chicago Outpatient Clinic, with an address at [name].

Prior to kidney transplantation many patients undergo hemodialysis treatments to sustain life. Hemodialysis is a process of purifying the blood of a person whose kidneys are not working normally. Arteriovenous fistula provides an access route for hemodialysis to be possible, by providing a direct connection of an artery to a vein. As part of standard of care at UIC, the AV fistula is ligated (a surgical procedure of closing off a blood vessel) at around one year post-transplant. As a way to retrieve bicep muscle biopsy samples we will retrieve samples during the closing AV fistulas (ligation) in kidney transplant patients with stable renal function. Patients will be consented with a supplemental consent for the bicep muscle biopsy.

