At baseline, after the patients have fasted overnight, blood samples will be drawn for analyses of pro-inflammatory cytokines such as C-reactive protein (CRP), IL-6, IL-1, TNF-alpha, homocysteine, adiponectin, leptin, and resistin as well as pro-regenerative cytokines such as TGF-beta and IL-10. Peripheral blood M1/M2 macrophages will also be measured. These tests will be performed at baseline, 6 months and 12 months post-intervention. Blood sampling will require approximately 20ml of blood at each blood draw. The total amount of blood drawn will be about 60 ml.

Metabolism and renal function changes

All patients will be monitored for fasting plasma Glucose, HbA1c, Lipid profile (Serum Cholesterol, Triglycerides, HDL Cholesterol, LDL Cholesterol), and serum creatinine during the study per standard of care for kidney transplant patients.

Vascular Function and Vascular Stiffness

Brachial FMD will be used to assess macrovascular endothelial function. This method involves the measurement of vascular reactivity of the brachial artery using non-invasive ultrasound technique. While the subject rests in the supine position, an 11 MHz probe will be used to determine brachial artery diameter above the antecubital fossa in the non-dominant arm. In addition, continuous wave Doppler will be used to determine brachial artery blood flow velocity. Brachial artery diameter and blood flow velocity will be measured under the following conditions: 1) At rest, 2) During reactive hyperemia produced by a five minute interruption of flow with a blood pressure cuff inflated >50mmHg above systolic pressure, 3) For three minutes after reactive hyperemia (30-second intervals for the first minute and 1-minute intervals thereafter).

Assessment of vascular stiffness using peripheral tonometry and ultrasound imaging
Upon entering the lab, participants will be required to rest quietly in the supine position in a dimly lit room for 10 minutes. Arterial size and stiffness will then be measured via ultrasonography using several different methodologies: 1) Pulse wave velocity: this test

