allows for a non-invasive way to measure arterial stiffness. Three disposable electrodes will be placed on the subject's torso. A pen-shaped transducer is placed over the carotid artery (side of the neck), over the femoral artery (top of the leg), over the anterior tibialis artery (inner ankle), and over the radial artery (wrist). The distance between each of these sites will be measured using a tape-measure. 2) Arterial Distensibility and function by ultrasound imaging: this test allows for non-invasive imaging of the carotid, brachial, and femoral arteries. Central blood pressure will be determined using the aforementioned pulse-wave analysis method (SphygmoCor SCOR, PWV Medical, Sydney, Australia). In brief, the pressure waveforms that are obtained at the radial artery site are subjected to a generalized transfer function to derive the corresponding central arterial waveforms

Cardio-ankle vascular index (CAVI) and Ankle Brachial Index (ABI)
CAVI and ABI will be assessed by pulse wave velocity analysis at the brachial and ankle arteries (VaSera VS 1500AU, Fukuda Denshi, Japan). The CAVI measurement requires the placement of ECG electrodes on both wrists, and a microphone for phonocardiography on the sternum in the second intercostal space, and 4 blood pressure cuffs. CAVI between the heart and ankle arteries is assessed using measurements of time between heart sound II and plethysmograms taken at the brachial and ankle arteries. This will be done to measure the stiffness of arteries and is independent of blood pressure. This test will be performed at baseline, 6 months and 12 months post-intervention.

Wrist Artery Stiffness

A very sensitive pen-shaped microphone will be placed on the subject's wrist (radial artery). This microphone measures how stiff the radial artery is. This test will be performed at baseline, 6 months and 12 months post-intervention.

Central Artery Stiffness

The same pen-shaped microphone used before will be placed on the subject's neck and then the artery at the top of their thigh. We will use these measurements to measure how stiff their central arterial system (the arteries in the midsection of the body) is. This test will be performed at baseline, 6 months and 12 months post-intervention.

Carotid Artery Stiffness and Compliance

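### Brachial FMD is tied to the non-dominant arm with no rule for a dialysis-fistula arm, although fistula status can change between the vascular tests

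*Combined protocol and SAP*

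**What the plan says.** All references are to the combined protocol and SAP.

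- **Arm for FMD.** Under Vascular Function and Vascular Stiffness, "an 11 MHz probe will be used to determine brachial artery diameter above the antecubital fossa in the non-dominant arm". The stimulus is a "five minute interruption of flow with a blood pressure cuff inflated >50mmHg above systolic pressure". Hand dominance is the only criterion for choosing the arm.
- **CAVI/ABI.** "CAVI and ABI will be assessed by pulse wave velocity analysis at the brachial and ankle arteries", with ECG electrodes, a microphone "on the sternum in the second intercostal space, and 4 blood pressure cuffs". Four cuffs at brachial and ankle sites imply one on each limb.
- **Radial tonometry.** The pulse-wave and wrist-stiffness paragraphs name no side.
- **Fistulas are expected.** Muscle Biopsy says that many patients had haemodialysis before transplant, that a fistula gives access for it, and that in standard care "the AV fistula is ligated (a surgical procedure of closing off a blood vessel) at around one year post-transplant". The sub-study takes patients with a brachial-cephalic fistula at the elbow or a brachial-basilic fistula in the arm, and collects the sample during ligation.
- **Biopsy timing.** Under Muscle Biopsy Inclusion, for the exercise arm "the biopsy will only be performed once, after the 12 month exercise intervention is completed"; for controls "this procedure will be performed once, around one year post transplant surgery (may occur at any time during the study". The Muscle Biopsy section instead requires controls to be at least one year post-transplant and limits the period to the 12 study months.
- **Start and visits.** Under Setting, training starts 2 months or more after transplant, with no upper limit. Vascular tests are at baseline, 6 and 12 months.
- **Analysis.** The Statistical analyses section plans unadjusted t-tests between groups.

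The vascular and cardiac test paragraphs, the exclusion criteria and the FMD cuff-risk paragraph contain no exception, arm switch or recording rule for a fistula arm.

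**The concern.** A fistula joins an artery directly to a vein. With a brachial-cephalic fistula at the elbow, a probe above the antecubital fossa images the artery that feeds it. Resting diameter and flow there depend on whether the fistula is open as well as on endothelial function. The same applies to arm-based stiffness values on that side, and possibly to cardiac ultrasound.

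If the fistula is open at baseline and closed at 12 months, the recorded change combines any training effect with the effect of closure. As the plan stands, nothing recorded would allow the two to be separated. At stake is the part of hypothesis 5 that predicts better peripheral vascular function.

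The cuff-risk paragraph for FMD mentions local discomfort, numbness and tingling. It does not say whether the cuff may go on an access arm.

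**Working it through.** The plan gives no power, SD or effect size for vascular outcomes, so there is no stated figure to reproduce. The allocation does check: 225 split 4:1 gives 180 and 45.

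**Step 1. Where routine ligation falls.** Inputs: ligation at about 12 months after transplant (Muscle Biopsy); start at *s* ≥ 2 months after transplant (Setting). Study month of ligation = 12 − *s*.

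| Start *s* (months after transplant) | Ligation (study month) | Baseline | Month 6 | Month 12 |
|---|---|---|---|---|
| 2 | 10 | open | open | closed |
| 4 | 8 | open | open | closed |
| 6 | 6 | open | changing | closed |
| 9 | 3 | open | closed | closed |
| 12 | 0 | at about closure | closed | closed |
| 15 | −3 | closed | closed | closed |

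Any start from 2 to just under 12 months puts routine ligation between the baseline and 12-month tests. A later start does not.

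**Step 2. Where biopsy ligation falls.** In GH it is at study month 12 or later. In controls, under the at-least-one-year condition, it runs from study month 12 − *s* to month 12: months 10–12 for *s* = 2, 6–12 for *s* = 6, 3–12 for *s* = 9. A control biopsy patient can therefore be ligated before the 12-month vascular tests, while a GH biopsy patient can still have an open fistula at them. The schedule table puts biopsy and vascular tests in the same 12-month column and gives no order.

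**Step 3. What this does to the comparison.** Let *p* be the share of patients with a fistula in the measured arm, *d* the shift on closure in SD units, and Δ the between-group difference in the share of those patients whose fistula closes between the two tests. None of these is in the documents. For illustration I assume *p* = 20–60% and *d* = 0.5–1.0 SD.

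- Within-group mean change from closure alone, if all close: *p* × *d* = 0.2 × 0.5 = 0.10 SD to 0.6 × 1.0 = 0.60 SD.
- Equal closure in both groups (Δ = 0): bias is 0 and the error rate stays at 5%. If half close (*q* = 0.5), variance is multiplied by 1 + *pq*(1 − *pq*)*d*², which is 1.022 to 1.21, a rise of about 2–21%.
- Unequal closure: bias = *p* × *d* × Δ. The inequality comes only from biopsy participants, so with similar biopsy uptake *f* among these patients in both groups, Δ cannot exceed *f*. The SE in SD units is √(1/180 + 1/45) = 1/6. At *f* = 25% the bias is at most 0.025–0.15 SD, with a two-sided false-positive rate of at most 5.3–14.7%. At *f* = 50% it is at most 0.05–0.30 SD and 6–44%. Uptake is not given either.

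For scale, 180 against 45 detects about (1.960 + 0.842)/6 = 0.47 SD at 80% power.

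**The case against.** The strongest reply is that efficacy is defined by differences between groups, and ligation at about one year is standard care in both. Randomisation should balance it. That stands: for routine ligation the cost to the planned comparison is precision.

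A reader might infer that any vascular difference between groups would reflect fistula closure instead of training. The documents do not support this. A between-group effect requires an optional biopsy, one of two fistula types, a fistula that affects the measured value, and different ligation timing relative to tests whose order is not stated. With a 2-month start, the control window before the 12-month tests is only study months 10–12.

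A reader might also infer that fistulas are usually open at baseline and closed at the end. That takes the earliest permitted start as typical, and no upper limit on the start is given.

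Nor can the number affected be derived. If 30–60% of patients had an upper-arm fistula and 70–80% of those were in the non-dominant arm, 225 × 0.3 × 0.7 = 47 to 225 × 0.6 × 0.8 = 108 patients would have FMD in a fistula arm. Those shares are assumptions, and the result counts patients measured in a fistula arm, not patients whose status changes between visits.

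Resting brachial pressure is left out of the point. The plan places it under a cited guideline that cannot be checked here.

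What survives is that the plan states a fixed arm rule which, followed as written, measures some patients on a fistula-feeding artery whose state may change between visits. That is more than a missing detail.

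**Conclusion.** The point holds in a limited form. The arm rule makes no provision for fistulas, and the plan's own dates put routine ligation inside the measurement window for starts from 2 to just under 12 months after transplant. In patients with the fistula on the measured side, FMD and arm-based stiffness changes cannot be read as training effects. Between groups, the expected consequence is added noise. Bias is possible only through the biopsy subset.

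The size is unknown. The ranges in the working rest on assumed prevalence, shift and uptake, and show only that the effect could run from negligible to relevant beside a detectable difference of 0.47 SD.

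Vascular function belongs to hypothesis 5 and is not named among the five efficacy criteria. BMI, lean/fat ratio and the other listed criteria are not touched by this point. It should be corrected because the correction is cheap and the information cannot be relied on to be recoverable afterwards.

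**What to change.** 1. **Arm rule.** In the FMD paragraph, replace the non-dominant-arm rule with: *the arm without current or previous dialysis access (the non-dominant arm if neither has had access), using the same arm at all three visits*. Apply the same side rule to radial tonometry and to the CAVI/ABI values that are analysed.
2. **Recording.** At each visit record fistula side, patency and ligation date. Cardiac ultrasound needs this too, since changing arms cannot protect it.
3. **Ordering.** Reconcile the two statements of biopsy timing (Muscle Biopsy Inclusion and Muscle Biopsy). Place the 12-month vascular and cardiac tests before any biopsy or ligation done at that visit, with the same ordering rule in both groups where possible. Testing first in GH alone would not close the gap if controls have already been ligated.
4. **Analysis.** Use baseline fistula status as a covariate for vascular and cardiac endpoints. Report patients with unchanged status as a sensitivity analysis only. Change in status arises after randomisation and may depend on group, so it should not be a primary covariate.
5. **Cuffs.** The investigators should state whether cuffs may be used on an access arm, and reconcile the FMD, CAVI/ABI and risk paragraphs with that statement.

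The cost is protocol wording and a few case-report-form fields. Some patients will be measured in the dominant arm, and those with access in both arms may have no suitable measurement.

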4. Patients with strength training will activate type II macrophages which are anti-inflammatory and pro-regenerative, tipping the balance away from inflammation towards regeneration when compared to the other treatment groups. Since strength training is likely to initiate signals of muscle regeneration, and since type II macrophages play a key role in this effect, it is possible that increasing the signaling to the muscle for regeneration may also increase the proportion of active type II macrophages which are anti-inflammatory. To test this hypothesis, we will test the proportion of peripheral blood M1/M2 macrophages at baseline, 6 months and 12 months after the initiation of the intervention. Recognizing that immunosuppression may significantly confound this proportion and overall suppress it, we will also test circulating levels of pro-inflammatory cytokines such as C-reactive protein(CRP), IL-6, IL-1, TNF-alpha, homocysteine, adiponectin, leptin, and resistin as well as pro-regenerative cytokines such as TGF-beta and IL-10.

5. We expect patients with strength training will experience less renal dysfunction, decreased hemoglobin A1C, increased peripheral vascular function, decreased fasting blood sugar when compared to the other treatment groups. The rationale for this hypothesis is the finding that muscle mass provides active regulation of glucose and other metabolites. Therefore increasing this may provide improved metabolic function. These laboratory panels are part of the standard transplant follow-up labs and add no cost to the project.

6. Patients with strength training will have an overall improved sense of well-being and energy level compared to those with physical therapy or no treatment. With twice weekly counseling for activity and nutrition, patients will be asked about their general health, mental health and pain intensity using the PROMIS questionnaires.

METHODS

Setting: The study will include 225 patients, to achieve a goal of 180 patients in the GH study group and 45 patients in the control group. Every patient will be followed for 3 years after the start of the intervention. Patients will start the intervention at least 2 months post-transplant; however they can be enrolled prior to transplant.

Main Study Inclusion criteria:

- Successful kidney transplantation (KTx) with primary graft function
- Age between 18 and 65 years

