Biodex: Bilateral isometric knee extensor and flexor peak torque will be measured using a Biodex System 3 dynamometer (Shirley, NY). Participants will be positioned in the dynamometer according to the manufacturer's recommendation. Briefly, the axis of rotation of the machine will align with the lateral epicondyle of the femur. The calf pad against which the participant exerts force will be positioned halfway between the lateral malleolus of the fibula and lateral epicondyle of the femur, and securely attached using straps. Straps will be placed over the thighs, pelvis, and torso regions to minimize movement during the test. We will use an anatomical reference position of 90° knee flexion, and isometric torque will be assessed at joint angles of 45°, 60°, and 75°. Peak torque will be obtained by having the participant perform 3 maximal contractions with the knee extensors for 5 seconds, which will be immediately followed by a 5 second maximal contraction with the knee flexors; 1 set will be performed. There will be no rest period between contractions within a set, and the rest period between each angle set will be 3 minutes. The highest recorded peak torque will be used as a measure of knee extensor and flexor isometric strength, and expressed as strength per body weight.

The 6 minute walk test involves walking as far as possible (down the hallway) over a six-minute period with distance recorded by researchers on one trial. During this test the subjects will wear a mask on their face that measures how much oxygen their body uses during this task (Cosmed K4b2, Rome, Italy). VO₂ will be assessed during this test to evaluate the amount of oxygen the subject's body utilizes during acts of regular daily activity, such as walking, which will be completed on a treadmill (as described below). Distance will also be collected as a way to measure the subject's functional capacity and to track progression. This test will be completed at baseline, 6 months and 12 months post-intervention.

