reporting done via the Lifestyle Inventory, understand their eating and sleeping patterns in greater detail by eliminating their opinions and emotional relationship and just focusing on actual intake, and provide a tool for ongoing monitoring and an opportunity for increasing patient's self-reflection on their food and sleeping habits. This will only be administered to the GH patients. Importantly, this is not a measurement tool that we would give at a specific time during the study; it is being used during the study by the research personnel and GH Method personnel to help manage self-reported behavior changes with the patients.

Counseling

Patients in the both arms will be counseled regarding weight loss per standard of care which consists of a pre-transplant and a post-transplant nutrition evaluation and education.

Video recording (optional)

Video recordings will be an option on the consent form for patients that are randomized into the GH exercise group. The option to be video recorded by the GH team at the beginning and end of the patient's 12 months of training. The recordings will be used to compare the progress of the patient from the beginning and end of GH training.

GH Study Visits:

At least one week prior to the first GH session with a patient, the written assessments will be completed and returned to GH personnel for scoring and processing. The first four GH sessions (over 2 weeks) for any patient will be 75 minutes. Following the first 4 sessions, ongoing patients will be slotted into recurring 60 minute time slots for the remaining 50 weeks. All of these visits will occur in the UIC Disability Health and Social Policy Building (DHSP) located at [name] in Suites 158, 190, and 195. The procedure visits at baseline, 6 and 12 months will take 2-3 hours.

At least twice per week, GH personnel will attempt to follow-up with patients via text message, email or a phone call to evaluate their physical recuperation and overall health and energy or to track their performance with a behavior change goal.

Patients will be asked to complete a physical regimen based on the following:

Summary of GH Study Visits:

- Patients may be asked to repeat previous weeks and/or skip a particular week depending on their energy, progress, and overall health.

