- Depending on a patient's individual physical need, mobility, the program may be slightly modified (number of repetitions, number of exercises, etc...) to be safe and appropriate for that individual.
- Each week comprises two different exercise days, each incorporating approximately 5-10 minute light warm-up plus stretching and then the exercises.
- Unless specified as a cardio or endurance week, all weeks consist of basic strength training/resistance workouts.

- The attached exercise list includes all possible strength training exercises, and clients complete the appropriate exercises for that week during their two, one-hour appointments each week. Depending on a patients particular physical health (e.g. shoulder problems) certain exercises may be eliminated or modified in terms of the safe range of motion and intensity.
- These sessions can be directly supervised by the GH instructors or performed by trained personnel implementing written instructions given by the instructors.

Week	Overview	Intensity/Weight	Breaks
Week 1	1 st Set: 30 Seconds with Only Safety Instruction 2 nd Set: 90 Seconds with More Focus on Form	Light	2 or more minutes
Week 2	1st Set: Holding at top and bottom of range (20 seconds each hold) 2 nd Set: 20 rep's and possible to add plus 5 depending on energy	Light	2 or more minutes
Week 3	1 st Set: Warm-Up of 15 repetitions 2 nd Set: Resistance focused 60 seconds, possible plus 5	Light/Moderate	2 or more minutes
Week 4	3 Sets for every exercise. Each set is 12 repetitions with some holding for five seconds.	Moderate	30 seconds between sets. 2 minutes between exercises.
Week 5	1 Warm Up Set of 15 repetitions. 1 Heavier Set of 11 Repetitions.	Moderate/Heavy	3 minute breaks
Week 6	Cardio Exercises (e.g. run in place). 5 different exercises are done as one round and two rounds total.	Light/Moderate	2 minutes between exercises and 4 minutes between rounds.
Week 7	1 st Set: Warm up of 12 repetitions. 2 nd Set: 6 repetitions	Moderate/Heavy	3 minutes
Week 8	1 Set: 90 seconds	Light	3 minutes
Week 9	1 Warm Up Set of 15 Repetitions. 3 Sets of 6-8 repetitions (depending on exercise)	Moderate/Heavy	3 minutes
Week 10	3 Sets of Declining Heaviness with 6 reps, 8 reps, and 10 reps	Moderate	3 minutes
Week 11	2 Sets Per Exercise without break between: 18 reps and 16 reps	Moderate/Light	2 minutes
Week 12	1 Set of 25 - 30 repetitions	Moderate/Light	2 minutes

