
The data will be entered into an Excel spreadsheet and stored on the UIMCC hospital server. The patient data, including age, sex, race, underlying kidney disease, length of hospital stay, rejection episode, comorbidities, and medications will be coded and patient names will not be included in the datasheet.

The de-identified collected data will be entered into a SAS database. Initial descriptive analysis will include calculating means, standard deviations, ranges and frequencies. T-tests for continuous variables and Chi Square or Fischer exact tests of association for

categorical variables will be used to compare results of the study between the two groups for the efficacy parameters listed above. A P value<0.05 will be considered significant.

6) Benefits/risks

The main risk of this research is loss of confidentiality of medical information. Consent will be obtained for all patients. Master patient code list will be kept in a separate file accessible only by the primary investigator. A member of the transplant team will be available to answer any questions or discuss any concerns that patients may have.

The patient may experience mild anxiety or discomfort in providing information about their health and well-being. The patient may also have a potential to feel anxiety when being video recorded (if applicable).

Risks associated with the exercise program

The likely risks and discomforts expected in this study are those that largely involve being engaged in an exercise program after a prolonged period of inactivity. Such risks include: strains, sprains, and muscle soreness. Serious physical injury is considered unlikely given the screening for inclusion and physician approval. We will attempt to reduce risks of injury and harm by promoting gradual increases in exercise across time throughout the 3 month period and having exercise be instructed and supervised by trained professional fitness personnel.

Risks associated with the blood draw:

The risks associated with a blood draw include: mild pain, bleeding or bruising at the site of the draw. In general, any bruising should completely disappear within several days. There are minimal risks of fainting or hypotension (low blood pressure) during or after the blood draw.

Risks associated with the Maximal Aerobic Capacity Test (VO2 Test) and the 6 minute walk test include:

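### Nothing keeps those who deliver the GH programme from testing outcomes, or masks testers and readers, so strength and vascular results are open to tester expectation

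*Combined protocol and SAP*

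**What the plan says.** All places are in the combined protocol and SAP.

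- **Arms.** Under Randomization, GH patients are coached for 12 months and controls receive standard care. There is no sham or attention control. The term open-label is not used, but patients and coaches must know the arm.
- **Who takes part in the intervention.** The Food Journal, given to GH patients only, is "used during the study by the research personnel and GH Method personnel to help manage self-reported behavior changes". Summary of GH Study Visits adds: "These sessions can be directly supervised by the GH instructors or performed by trained personnel implementing written instructions given by the instructors". Neither research personnel nor trained personnel is defined.
- **Effort-dependent tests.** For Biodex, "Peak torque will be obtained by having the participant perform 3 maximal contractions with the knee extensors for 5 seconds", and the highest value counts. The 6-minute walk is "walking as far as possible (down the hallway) over a six-minute period with distance recorded by researchers on one trial". In the VO2 max test the workload rises until effort is maximal, and no criterion for maximal effort is given.
- **Operator-dependent tests.** FMD, carotid and cardiac ultrasound are taken with a hand-held probe. No reader is named and no reading rule is given.
- **Testing staff.** Section 6 (Benefits/risks) requires CPR and emergency training and refers to one department's procedures. It does not mention independence from session delivery.
- **Masking.** No section provides for a masked assessor or a masked reader.

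**The concern.** Patients in an exercise trial cannot be masked, but testers and readers often can be, and the plan does not use this option. Maximal torque and walking distance respond to encouragement. VO2 max depends on when effort is judged maximal. Ultrasound diameters depend on how they are acquired and measured. A tester who knows the arm, and perhaps has coached the patient, could push these results towards GH without intending to.

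Such a shift would add to the GH-control difference and would look like a treatment effect. A larger sample would not remove it, and randomisation does not protect against bias that arises at later visits. Masking cannot be added once the tests have been done.

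**Working it through.** **1. Is there a safeguard elsewhere?** Two provisions come close. Section 5 (Statistical analyses) codes the data and leaves names out of the datasheet, but this follows measurement. Section 6 appoints an unaffiliated physician for safety, and that person neither tests nor reads. Neither provision fills the gap.

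**2. Which outcomes are exposed?**

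| Outcome | Place in the plan | Exposed to tester or reader? |
|---|---|---|
| Biodex strength | Hypothesis 2 | Yes |
| Peripheral vascular function | Hypothesis 5 (tests not named there) | Yes, where measured by hand, as in FMD |
| 6-minute walk, VO2 max, cardiac ultrasound | Measured; in no hypothesis | Yes |
| Lean/fat ratio, BMI, inflammatory and metabolic parameters | Efficacy list, Section 5 | Little |
| Perception of well-being | Efficacy list, Section 5 | Self-reported; masked testers would not remove response bias |

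None of the outcomes in the first three rows is on the Section 5 efficacy list.

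**3. Inputs for the size.** From the documents:
- Setting: "The study will include 225 patients, to achieve a goal of 180 patients in the GH study group", with 45 controls.
- Randomization: patients "will be randomized 4:1 to the GH group or the control group". Check: 225 × 4/5 = 180 and 225 × 1/5 = 45, which agree.
- Section 5: "T-tests for continuous variables and Chi Square or Fischer exact tests of association" and "A P value<0.05 will be considered significant". Sidedness is not stated, so two-sided is assumed.

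The plan gives no effect size, SD, power or dropout rate, so the total of 225 cannot be reproduced.

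**4. Standard error of the difference, in SD units.**
SE = √(1/180 + 1/45) = √(0.00556 + 0.02222) = 0.1667.
An observed difference of 1.96 × 0.1667 = 0.33 SD reaches P<0.05.

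**5. False-positive rate under an assumed bias b, with no true effect.**
Rate ≈ P(Z > 1.96 − b/SE) + P(Z < −1.96 − b/SE).

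| Assumed b (SD) | b/SE | Normal approximation, 180 v 45 | Noncentral t, 180 v 45 | Noncentral t, 144 v 36 |
|---|---|---|---|---|
| 0 | 0 | 5.0% | 5.0% | 5.0% |
| 0.1 | 0.6 | 9.2% | 9.2% | 8.3% |
| 0.2 | 1.2 | 22.4% | 22.3% | 18.7% |
| 0.3 | 1.8 | 43.7% | 43.4% | 36.0% |

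The last column assumes 20% dropout: 180 × 0.8 = 144 and 45 × 0.8 = 36. The documents give no value for b, so every row with b above 0 is illustrative.

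**The case against.** **Overlap is not shown.** The Food Journal sentence names research personnel and GH Method personnel as two groups, and it also says that the journal is not a measurement tool. Those who may give sessions are nowhere said to test. A reader might infer that coaches run the 12-month Biodex or read the FMD images. The documents do not support that. They only fail to rule it out. This part of the objection stands.

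**The main efficacy list is mostly untouched.** Section 5 applies its tests to well-being, lean/fat ratio, BMI, inflammatory and metabolic parameters. A reader might conclude that tester bias threatens the efficacy claim as a whole. It does not: the point is confined to two hypothesis outcomes and some measured outcomes outside the hypotheses. This also stands.

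**The tests are already partly standardised.** Biodex has fixed positioning, angles, number and length of contractions, and rest. Treadmill speed and incline are set, as are FMD cuff time and measurement intervals. DEXA is a whole-body scan run to the manufacturer's guidelines, and no defect is alleged there. These details leave less room for bias, but they do not cover encouragement, the judgement of maximal effort, or who measures the images.

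**Direction and timing are assumed.** It is tempting to say that the bias must favour GH and must arise only after baseline. The documents establish neither. They do not say that baseline testing precedes randomisation, and some GH-only assessments are given at enrolment, so arm may already be known at baseline.

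**Conclusion.** The omission is real and worth correcting, within limits. Arm is evident, research personnel share in managing GH patients' behaviour change, and no rule separates delivery from testing or masks testers or readers. Followed as written, the plan leaves Biodex strength and peripheral vascular function open to tester expectation, along with the 6-minute walk, VO2 max and cardiac ultrasound.

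The bias could favour GH, but its size is unknown. For shifts of 0.1 to 0.3 SD, the two-sided P<0.05 rate would rise from 5% to between about 9% and 44% at 180 v 45, or between about 8% and 36% with 20% dropout. This assumes no true effect, a constant shift towards GH, and use of the plan's t-test for outcomes that are not on its efficacy list. The figures show sensitivity; they do not estimate what will happen.

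**What to change.** Add three rules under Parameters to analyze in all patients:

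1. Nobody who delivers GH sessions, follow-up messages or Food Journal review tests that patient at 6 or 12 months. Where existing staffing allows, testers are not told the arm and patients are asked not to disclose it.
2. Biodex, the 6-minute walk and VO2 max use one fixed encouragement script and fixed criteria for a completed test, at every visit and in both arms. These criteria concern measurement only and do not touch ending a test for safety.
3. FMD, carotid and cardiac ultrasound recordings are saved and measured by existing staff under study code, with arm and visit removed.

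DEXA needs no change on this point.

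**Cost.** Rules 2 and 3 need a script, file labelling and later reading of images, with no new procedure for patients. Rule 1 makes scheduling less flexible. If the teams are already separate, it only writes down current practice; if they overlap, it is harder to apply, which is why masking of testers is tied to existing staffing.

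**What remains.** Some patients will disclose their arm. Coded reading does not mask the person who acquires the images. Response bias in self-reported well-being is not addressed.
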